24. APPENDIX V. MINIMUM MADRS TOTAL SCORE CRITERIA AT BASELINE

To be eligible for randomization, Baseline (Visit 2) MADRS total score must be ≥ 22 AND no more than a 25% decrease from the total score at Screening. (Refer to Table below for reference.)

The following formula is to be utilized to determine the MADRS total score change at Baseline (Visit 2):

$$\frac{\text{MADRS total score at Screening} - \text{MADRS total score at Baseline}}{\text{MADRS total score at Screening}} \times 100\%$$

MADRS total score at Screening (V1)	MINIMUM Permissible MADRS total score at Baseline (V2)	MADRS total score at Screening (V1)	MINIMUM Permissible MADRS total score at Baseline (V2)
22	22	42	32
23	22	43	33
24	22	44	34
25	22	45	34
26	22	46	35
27	22	47	36
28	22	48	37
29	22	49	37
30	23	50	38
31	24	51	39
32	25	52	40
33	25	53	40
34	26	54	41
35	27	55	42
36	28	56	43
37	28	57	43
38	29	58	44
39	30	59	45
40	31	60	46
41	31	-	-

1. INTRODUCTION

This document describes the rules and conventions to be used in the presentation and analysis of efficacy and safety data for Protocol SEP380-201. It describes the data to be summarized and analyzed, including specifics of the statistical analyses to be performed.

Data and Safety Monitoring Board (DSMB) analysis plan will be described in separate documents. A Blind Data Review (BDR) Plan will be written to describe the process and the outputs to be delivered during the IPD/BDR meetings.

This statistical analysis plan (SAP) is based on protocol version 2.0, dated 04 June 2018. Specific amendments were developed for Japan (version 2.01A dated 29 January 2019) and Poland (version 2.00B dated 18 January 2019) Hereafter, this protocol version is referred to as the Clinical Study Protocol (CSP). This SAP covers both the United States/European Union (US/EU) sites analysis, the Japan sites analysis and their pooled analysis.

2. STUDY OBJECTIVES

2.1. PRIMARY OBJECTIVE

The primary objective is to evaluate the efficacy of SEP-4199 200 mg/day and 400 mg/day compared with placebo for major depressive episode associated with bipolar I depression (diagnosed by DSM-5 criteria) as measured by Montgomery-Asberg Depression Rating Scale (MADRS) total score.

2.2. SECONDARY OBJECTIVES

The secondary objective is to evaluate the effect of SEP-4199 200 mg/day and 400 mg/day compared with placebo on severity of illness as measured by the Clinical Global Impression Bipolar Version, Severity of Illness (CGI-BP-S) score (depression).

2.3. PHARMACOKINETIC OBJECTIVES:

The pharmacokinetic objectives are:

- To evaluate the therapeutic plasma concentration range of SEP-4199 200 mg/day and 400 mg/day for major depressive episode associated with bipolar I disorder.
- To determine the population PK of SEP-4199 200 mg/day and 400 mg/day.

2.4. OTHER OBJECTIVES

Other objectives for the study include:

Document:

Author:

Version Number:

V2.0

Version Date:

21MAY2020

Template No: CS_TP_BS016 Revision 4
Effective Date: 01Apr2016

Reference: CS_WI_BS005

- To determine the relationship between SEP-4199 PK and plasma prolactin for SEP-4199 200 mg/day and 400 mg/day.
- To characterize the exposure-response relationship of SEP-4199 200 mg/day and 400 mg/day and symptoms as measured by MADRS using population PK/PD.
- To evaluate the effect of SEP-4199 200 mg/day and 400 mg/day compared with placebo on anxiety symptoms, as measured by the Hamilton Rating Scale for Anxiety (HAM-A).
- To evaluate treatment response, defined as $\geq 50\%$ reduction from baseline on the MADRS total score.
- To evaluate the effect of SEP-4199 200 mg/day and 400 mg/day on symptom remission, defined as a MADRS total score of ≤ 12 after 6 weeks of treatment.
- To evaluate the effect of SEP-4199 200 mg/day and 400 mg/day on functional impairment associated with bipolar depressive symptoms, as measured by the Sheehan Disability Scale (SDS) total score.
- To evaluate the effect of SEP-4199 200 mg/day and 400 mg/day on symptom severity as measured by the Quick Inventory of Depressive Symptomatology – Self Report (QIDS-SR16) total score.

2.5. SAFETY OBJECTIVES

The safety objectives are:

- To evaluate the effect of SEP-4199 200 mg/day and 400 mg/day on treatment-emergent mania, as assessed by the Young Mania Rating Scale (YMRS) or an adverse event (AE) of mania or hypomania.
- To evaluate safety and tolerability of SEP-4199 200 mg/day and 400 mg/day as measured by physical examinations, 12-lead electrocardiograms (ECG) parameters, vital signs, AE reports, clinical laboratory results, Columbia-Suicide Severity Rating Scale (C-SSRS), Abnormal Involuntary Movement Scale (AIMS), Barnes Akathisia Rating Scale (BARS), and the Modified Simpson-Angus Scale (SAS).

2.6. STUDY ENDPOINTS

2.6.1. PRIMARY EFFICACY ENDPOINT:

- Change from baseline in MADRS total score at Week 6.

Document:

Author:

Version Number:

V2.0

Version Date:

21MAY2020

Template No: CS_TP_BS016 Revision 4
Effective Date: 01Apr2016

Reference: CS_WI_BS005

2.6.2. SECONDARY EFFICACY ENDPOINT:

- Change from baseline in global severity assessed by the CGI-BP-S score (depression) at Week 6.

2.6.3. PHARMACOKINETIC ENDPOINTS:

- Plasma concentrations of R-amisulpride and S-amisulpride.
- Plasma concentrations of prolactin.

2.6.4. OTHER ENDPOINTS:

- Number and percentage of treatment responders, defined as $\geq 50\%$ reduction from baseline in MADRS total score at Week 6.
- Time to treatment response, defined as $\geq 50\%$ reduction from baseline MADRS total score.
- Change from baseline in anxiety symptoms based on the HAM-A total score at Week 6.
- Incidence of symptom remission, defined as a MADRS total score of ≤ 12 at Week 6.
- Time to remission, defined as MADRS total score of ≤ 12 .
- Functional impairment assessed by change from baseline in the SDS total score at Week 6.
- Subject self-report of overall depressive symptom severity, assessed by change from baseline in the QIDS-SR16 total score at Week 6.

2.6.5. SAFETY ENDPOINTS:

- Incidence of treatment-emergent mania, defined as a YMRS score of ≥ 16 on any 2 consecutive visits or at the final assessment, or an AE of mania or hypomania.
- Incidence of AEs, discontinuation due to AEs, and serious AEs (SAEs).
- Changes in weight, clinical laboratory tests, vital signs, and ECG measurements.
- Change from baseline in AIMS, BARS, and Modified SAS.
- Frequency and severity of suicidal ideation and suicidal behavior using the C-SSRS.

Document:

Author:

Version Number:
Version Date:

V2.0

21MAY2020

Template No: CS_TP_BS016 Revision 4
Effective Date: 01Apr2016

Reference: CS_WI_BS005

3. STUDY DESIGN

3.1. GENERAL DESCRIPTION

[figure not shown]
This is a randomized, double-blind, placebo-controlled, parallel-group, fixed-dose study designed to evaluate the efficacy, safety, and tolerability of treatment with SEP-4199 monotherapy given as 200 mg/day or 400 mg/day compared with placebo for the treatment of major depressive episode associated with bipolar I disorder (bipolar I depression). The study is projected to randomize approximately 294 subjects (98 subjects per treatment group) in the US and Europe to one of 3 treatment groups in a 1:1:1 ratio (SEP-4199 200 mg/day or 400 mg/day, or placebo).

In addition, a Japanese cohort will be included in the study to summarize efficacy and safety data for Japanese subjects with bipolar I depression. Approximately 45 subjects (15 subjects per treatment group) will be randomized in the Japanese cohort in a 1:1:1 ratio (SEP-4199 200 mg/day or 400 mg/day, or placebo).

The study will consist of a Screening period (up to 21 days), a 6-week treatment period (42 days), and a follow-up period (7 [\pm 2] days after the last study drug dose). The screening visit will be defined as Visit 1, the Baseline/Week 0 visit will be defined as Visit 2, Weeks 1, 2, 4, and 6 will be defined as Visits 3-6, respectively, and the Follow-up/Week 7 visit will be defined as Visit 7 (Table 2).

A study schematic is presented in Figure 1. Details of the study assessments and other procedures to be performed at each visit are presented in Table 2 and Section 11 of the CSP. If necessary, subjects may return to the clinic at any time for an unscheduled visit.

Figure 1 Study Schematic – All Subjects

Document:

Author:

Version Number:
Version Date:

V2.0

21MAY2020

Template No: CS_TP_BS016 Revision 4
Effective Date: 01Apr2016

Reference: CS_WI_BS005

3.2. METHOD OF ASSIGNING SUBJECTS TO TREATMENT GROUPS

Randomization will be stratified by region. The treatment schedule will be generated by a non-study biostatistician. Once a subject is deemed eligible to be randomized at Day -1, an interactive voice/web-based system (IXRS) will perform the treatment assignment. Subjects will be randomized to 1 of 3 treatments in a 1:1:1 ratio:

- SEP-4199 200 mg/day
- SEP-4199 400 mg/day
- Placebo QD

3.3. BLINDING

Subjects, Investigators, clinical site staff, persons performing the assessments, clinical operations personnel (including the sponsor's bioanalytical manager), data analysts, and personnel at central laboratories (including imaging) will remain blinded to the identity of the treatment from the time of randomization until unblinding, using the following methods:

- Randomization data are kept strictly confidential until the time of unblinding, and will not be accessible by anyone involved in the study with the following exceptions: bioanalytical laboratory personnel involved in the analysis of PK samples, DSMB members involved in regular review of safety data, external statistical staff involved in preparing materials for DSMB reviews, and the Sponsor's clinical trials materials management.
- Prolactin levels will be blinded except for results from Visit 1 (Screening).

The identity of the treatments will be concealed by the use of study drugs that are all identical in packaging, labeling, schedule of administration, and appearance.

Plasma concentrations of R-amisulpride, S-amisulpride, and total amisulpride will not be disclosed before unblinding. In the event that concentration data transfer to the sponsor becomes necessary prior to the database lock, then the concentration data can only be shared with the sponsor's bioanalytical project manager with dummy subject IDs.

In the case of a medical emergency where knowledge of study drug by the Investigator or an authorized delegate is essential for immediate medical management, a 24-hour code-break service will be available via the IXRS. The date and reason for unblinding are to be documented. Any subject for whom the treatment assignment was unblinded is to be discontinued from further study participation. The subject should return for a final study assessment. The identity and responsibility of those individuals at the study site who gain access to the unblinded treatment assignment must be documented. It is mandatory that all personnel who are involved in the unblinding, and who have access to the unblinded treatment assignment, maintain the confidentiality of the information and do not divulge the treatment assignment.

Document:

Author:

Version Number:
Version Date:

V2.0

21MAY2020

Template No: CS_TP_BS016 Revision 4
Effective Date: 01Apr2016

Reference: CS_WI_BS005

3.4. DETERMINATION OF SAMPLE SIZE

A total sample size of 279 evaluable subjects in US and Europe (93 per treatment group: SEP-4199 200 mg/day, SEP-4199 400 mg/day, and placebo) with a global 2-sided alpha of 0.05 will provide about 90% power to reject at least 1 truly significant primary comparison and about 75% power to reject both truly significant primary comparisons using the truncated Hochberg ($\gamma = 0.9$) procedure, assuming treatment effect sizes of 0.44 for both doses of SEP-4199. The effect sizes were selected considering the data from the completed Lurasidone bipolar depression monotherapy study (Loebel 2014). This effect size corresponds to a treatment difference of -3.85 for a SEP-4199 dose with a common standard deviation of 8.745 on the MADRS scale change from baseline at Week 6. An upward adjustment of approximately 5% is used to compensate for information lost due to subjects who are randomized and do not provide any postbaseline primary efficacy data. The total sample size will be approximately 294 randomized subjects (or $N = 98$ subjects per treatment group).

For the secondary efficacy endpoint, assuming the 93 subjects per treatment arm, the study will have 71% power to reject at least one truly significant comparison within the CGI-BP-S family using the regular Hochberg procedure, given a treatment difference of -0.47 for a SEP-4199 dose with a common standard deviation of 1.24 on the CGI-BP-S change from baseline at Week 6. The correlation between the primary and the secondary endpoint is assumed to be 0.8 for each treatment arm.

The sample size was calculated using the Mediana package version 1.05 within R version 3.4.2 ([R Core Team 2017](#))

See [APPENDIX 4](#) for additional power and Type I error rate calculations.

The sample size for the Japanese cohort (45 total [$N = 15$ subjects per group], including 9 dropouts) provides more than 80% probability to have a treatment difference point estimate greater than zero for the MADRS.

3.5. CHANGES IN THE CONDUCT OF THE STUDY

There are no anticipated changes from the protocol in the conduct of the study.

3.6. SCHEDULE OF EVENTS

Schedule of events can be found in Section 1, Table 2 Schedule of Assessments of the CSP.

3.7. CHANGES TO ANALYSIS FROM PROTOCOL

The following changes to analysis from protocol are conducted:

- During the BDR Meeting, it was determined that there were 3 subjects who were randomized but never received a dose and 4 more subjects who were randomized, received a dose, but did not have any postbaseline MADRS/CGI data. To be consistent with the previous Sunovion Central Nervous System (CNS) studies, the definition of the intention-to-treat (ITT) population was subsequently changed from "subjects who are randomized" to

Document:

Author:

Version Number:

V2.0

Version Date:

21MAY2020

Template No: CS_TP_BS016 Revision 4
Effective Date: 01Apr2016

Reference: CS_WI_BS005

“subjects who are randomized, received at least one dose of study medication, and have a baseline and at least one post-baseline efficacy measurement in MADRS Total Score or CGI-BP-S Depression Score”.

- During the dry run 2 draft output review, some baseline characteristic tables (exposure, compliance, psychiatric and medical history) were decided to be only created for the Safety Population as the difference of subjects between the ITT and Safety populations does not affect the interpretation of the results.
- MedDRA dictionary version 19.1 was used for AE, MH and psychiatric disorders coding instead of version 20.1 (or higher) as indicated in protocol.
- WHO-DD dictionary version 01MAR2017 was used for medications coding instead of version 01SEP2017 (or more recent) as indicated in protocol.
- It was stated in the protocol that the methodology and results of the population pharmacokinetic/pharmacodynamic analyses and the relationship between SEP-4199 PK and plasma prolactin were to be described in a separate document from this SAP and reported as an appendix to the CSR. The analyses will be reported separately from the CSR.
- ECG markedly abnormal criteria Categories were updated in SAP to be more inclusive than in protocol by changing ‘>’ to ‘≥’.

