15.2. Analysis Populations

Each population below will be created for both the US and Europe cohort and the Japanese cohort.

Intention-to-Treat Population: The intention-to-treat (ITT) population will consist of subjects who are randomized. Subjects are included in the ITT population regardless of any protocol deviations. Subjects will be analyzed according to their randomized treatment group. The ITT population is the primary population for all efficacy analyses.

Per Protocol Population: These are all ITT subjects who have no important protocol deviations that may affect the interpretation of the primary efficacy endpoint as defined in [Section 15.3.3](#). Subjects in the Per Protocol population will be analyzed according to their randomized treatment group.

Analysis of the primary and the secondary efficacy endpoints will also be performed using the Per Protocol population.

Safety Population: The safety population will consist of all subjects who randomized and receive at least one dose of study medication. Subjects will be analyzed according to the predominant treatment received. The predominant treatment is defined as the treatment to which the subject is exposed for the greatest duration during the treatment period. This will generally be the same as the randomized treatment group, unless the subject takes incorrect study medication during their entire participation in the study.

Pharmacokinetic (PK) Population: The PK population includes the Safety population subjects who have at least 1 valid postdose PK concentration value without protocol deviations or events with the potential to affect PK. The PK analysis will be based on the PK population.

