5.1. INTENTION-TO-TREAT [ITT] POPULATION

The intention-to-treat (ITT) population will consist of subjects who are randomized, received at least one dose of study medication, and have a baseline and at least one post-baseline efficacy measurement in MADRS Total Score or CGI-BP-S Depression Score. Subjects are included in the ITT population regardless of any protocol deviations. Subjects will be analyzed according to their randomized treatment group.

The ITT population is the primary population for all efficacy analyses.

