16.1.4.2. Pattern-mixture model with placebo-based multiple imputation

All ITT subjects are included in pattern-mixture model with placebo-based multiple imputation.

The MMRM model used in the primary analysis makes the assumption that data are MAR. However, the missing data mechanism may or may not be at random. Sensitivity to the missing data assumption will be tested by using the PMM with placebo-based multiple imputation method, exploring the robustness of the MMRM results of the primary efficacy analysis. In this analysis, missing values in the SEP-4199 (200 or 400 mg/day) treatment groups after remapping of the ET visits will be imputed based on data of the placebo group, assuming that after withdrawal, subjects from the SEP-4199 (200 or 400 mg/day) group will exhibit the same future evolution of depressive episode as subjects from the placebo group, and that subjects who discontinue from the placebo group will exhibit the same future evolution of depressive episode as subjects in the placebo group remaining in the study. This approach does not assume a sustained benefit of experimental treatment after discontinuation.

Two separate imputation procedures are used to impute missing values. Firstly, the Markov chain Monte Carlo (MCMC) method is used to perform partial imputation to obtain datasets with monotone missing patterns. Then a sequential regression multiple imputation method is used to impute the monotone missing values.

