16.3.1.5. MADRS responders

A MADRS responder is defined as achieving a $\geq 50\%$ reduction from the baseline total score at Week 6. The MADRS total score percentage change will be defined as $(\text{value at postbaseline visit} - \text{baseline value}) \times 100 / (\text{baseline value})$. Subjects having a negative percentage change indicate improvement in MADRS total score.

Any ITT subject with missing response at Week 6 will be classified as non-responder. As a sensitivity analysis, the same analysis will be repeated by excluding subjects with missing responses, where applicable.

In addition, the following endpoints will be explored through graphing:

- Subjects achieving a $\geq 40\%$ reduction from the baseline total score at Week 6;

Document:

Author:

Version Number:

V2.0

Version Date:

21MAY2020

Template No: CS_TP_BS016 Revision 4
Effective Date: 01Apr2016

Reference: CS_WI_BS005

- Subjects achieving a $\geq 30\%$ reduction from the baseline total score at Week 6;
- Subjects achieving a $\geq 20\%$ reduction from the baseline total score at Week 6.

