16.3.1.6. MADRS remission

A MADRS remission is defined as a MADRS total score of ≤ 12 at Week 6.

Any ITT subject with missing MADRS total score at Week 6 will be classified as non-remitter. As a sensitivity analysis, the same analysis will be repeated by excluding subjects with missing MADRS total score at Week 6, where applicable.

Additionally, subjects with MADRS total scores ≤ 10 and ≤ 8 at Week 6 are of interest.

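### The SAP's redefined ITT set excludes 7 randomized subjects, so the missing-equals-failure responder and remission analyses no longer cover everyone randomized; the likely effect is about one point, direction unknown

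*SAP*

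**What the plan says.** Protocol 15.2: "The intention-to-treat (ITT) population will consist of subjects who are randomized". The same section makes ITT the primary population for all efficacy analyses.

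SAP 3.7 describes two groups found at the blinded data review (BDR) meeting. Of the first group it says that "there were 3 subjects who were randomized but never received a dose". The second group, counted separately from the first, is "4 more subjects who were randomized, received a dose, but did not have any postbaseline MADRS/CGI data". It then says that "the definition of the intention-to-treat (ITT) population was subsequently changed from" all randomized subjects to a narrower set. SAP 5.1 requires that ITT subjects be randomized, have taken a dose and "have a baseline and at least one post-baseline efficacy measurement in MADRS Total Score or CGI-BP-S Depression Score". The reason given is consistency with the sponsor's previous CNS studies.

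SAP 16.3 analyses all other efficacy endpoints in ITT. Two of them use failure imputation:
- SAP 16.3.1.5: "Any ITT subject with missing response at Week 6 will be classified as non-responder".
- SAP 16.3.1.6: "Any ITT subject with missing MADRS total score at Week 6 will be classified as non-remitter".

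The missing-data sensitivity analysis for both endpoints drops subjects whose Week 6 value is missing. SAP 16.3.3.5 and 16.3.3.6 add a version without remote visits.

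For the MNAR analyses of the primary endpoint, SAP 16.1.4.2 says "All ITT subjects are included in pattern-mixture model with placebo-based multiple imputation". SAP 16.1.4.3 gives the tipping-point analysis the same population.

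**The concern.** An MMRM on change from baseline cannot use a subject with no post-baseline value, so the narrower set costs it essentially nothing. A failure-imputed binary endpoint is different. It is built to keep everyone in the denominator, and a subject with no follow-up is the clearest case for it. With the rule tied to the new ITT, these 7 subjects are left out instead of being counted as failures. The one missing-data sensitivity analysis for these endpoints removes more subjects, so nothing listed shows the result for all randomized subjects. The number needed to treat in SAP 16.3.3.5 is derived from the same rates.

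The two imputation analyses could also use these subjects. SAP Appendix 3 starts the imputation from baseline MADRS and expects no missing baseline values. SAP 6.2 still defines a baseline for subjects randomized but not treated, who can no longer be in ITT.

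At stake is a post-randomization exclusion, under the name ITT, in analyses that do not need it.

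**Working it through.** **Inputs from the documents**
- 294 planned US/Europe subjects, 98 per arm; 93 per arm evaluable; effect size 3.85/8.745 = 0.44; truncated Hochberg with gamma 0.9; global two-sided alpha 0.05 (SAP 3.4).
- 45 planned Japanese subjects (SAP 3.4), so 339 overall.
- 3 + 4 = 7 excluded subjects (SAP 3.7), arm and cohort not given.

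**Assumptions.** The documents give no response rates, so I take 30-50% on placebo and 10 to 20 points more on active. All 7 are placed in the US/Europe cohort, which is the worst case.

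**1. The plan's own figures.** At one-sided 0.025 the truncated Hochberg critical values are 0.95 x 0.025 for the larger p-value and 0.025/2 for the smaller. Simulating two z-tests that share a placebo arm (400,000 runs, 93 per arm) gives power 0.904 for at least one dose and 0.752 for both. The plan states about 90% and 75% (Appendix 4: 0.9027 and 0.7517). Inflation: 93/0.95 = 97.9, rounded up to 98 per arm, 294 in total. Both reproduce.

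**2. Number excluded.** 7/294 = 2.4%, or 7/339 = 2.1% with Japan. The inflation allowed for 294 - 279 = 15 subjects without post-baseline data. With 287/3 = 95.7 per arm, design power would be 0.912 and 0.765, so primary power is not harmed.

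**3. Shift in the risk difference.** Let p1 and p0 be the active and placebo response rates with all 98 per arm counted. Removing k1 active and k0 placebo non-responders changes the risk difference by

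p1 x k1/(98 - k1) - p0 x k0/(98 - k0).

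Examples, with the range over all assumed rates in the last column:

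| Removed (active, placebo) | Example | Shift | Range (points) |
|---|---|---|---|
| 3, 2 | 69/98 vs 49/98 becomes 69/95 vs 49/96: 20.4 to 21.6 | +1.2 | +0.6 to +1.2 |
| 2, 3 | 59/98 vs 49/98 becomes 59/96 vs 49/95: 10.2 to 9.9 | -0.3 | -0.3 to +0.1 |
| 4, 0 | 69/98 vs 49/98 becomes 69/94 vs 49/98: 20.4 to 23.4 | +3.0 | +1.7 to +3.0 |
| 0, 4 | 69/98 vs 49/98 becomes 69/98 vs 49/94: 20.4 to 18.3 | -2.1 | -1.3 to -2.1 |
| 7, 0 | 69/98 vs 49/98 becomes 69/91 vs 49/98: 20.4 to 25.8 | +5.4 | +3.1 to +5.4 |
| 0, 7 | 69/98 vs 49/98 becomes 69/98 vs 49/91: 20.4 to 16.6 | -3.8 | -2.3 to -3.8 |

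**4. Nominal p-values** (pooled two-proportion z-test, a simpler test than the planned logistic regression). Uneven splits can cross 0.05 in either direction:
- 59/98 vs 49/98, p = 0.151; with 7 active removed (59/91), p = 0.040.
- 54/98 vs 39/98, p = 0.032; with 7 placebo removed (39/91), p = 0.093; with 4 placebo removed (39/94), p = 0.059.

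**5. How likely is the extreme split?** If each subject is equally likely to be in any arm, the chance that all 7 share one arm is 3 x (1/3)^7 = 1/729, about 0.14%.

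**6. Placebo-based imputation.** Suppose 7/3 = 2.3 of the 98 subjects in an active arm are added with zero effect instead of -3.85. The estimate moves by about 3.85 x 2.3/98 = 0.09 MADRS points, against a planning standard error of 8.745 x sqrt(2/98) = 1.25.

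**The case against.** The change is openly reported in SAP 3.7 with counts and a reason. It followed a blinded review, and SAP section 5 and Appendix 6 require populations and changes to be settled before unblinding. That stands, and no bias from knowledge of treatment is alleged.

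A reader might infer that the redefinition cancels the plan's failure rule. The documents do not show this. The rule is written for ITT subjects and still catches every ITT subject whose Week 6 score is missing. The protocol's responder section (15.3.5.3) has no such rule and SAP version 1 is not available, so nothing shows that the rule ever covered these 7.

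A reader might also infer that the 7 are probable treatment failures. No reason for the missing data is given, and 3 were never dosed. The argument needs only the SAP's own convention that missing counts as failure.

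Nor are the MNAR analyses less strict than the SAP states. They are specified for ITT as the SAP defines it, and keeping the primary analysis population is a coherent choice. Extending them is optional.

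Finally, SAP section 9 already reports subjects randomized but not dosed by group, and the size of each population. A reader could rebuild a crude all-randomized rate from these, but not the adjusted odds ratio.

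What remains is that the protocol's population was narrowed after the 7 had been counted, and that no listed responder or remission analysis uses all randomized subjects.

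**Conclusion.** The point holds as a minor one. The SAP's ITT is narrower than the protocol's by up to 7 US/Europe subjects, and the failure-imputed responder and remission analyses therefore omit them. Under the assumed rates the risk difference shifts by -0.3 to +1.2 points with a near-even split, and by at most +5.4 or -3.8 points if all 7 were in one arm. The direction is unknown: exclusions from active flatter the drug and exclusions from placebo do the reverse.

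The p-value crossings in the working should not be read as a likely change of conclusion. They need uneven splits and effects close to the threshold, and both endpoints lie outside the multiplicity procedure in SAP 7.4. The primary and secondary MMRM are essentially unchanged. I say essentially because the SAP does not state in words that the 3 never-dosed subjects have no post-baseline scores.

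**What to change.** 1. Label the current set modified ITT and keep it for the MMRM analyses.
2. Run responder and remission on all randomized US/Europe subjects with missing counted as failure, at least as a sensitivity analysis. The planned logistic model needs only treatment, region and baseline MADRS, and the SAP expects baseline MADRS to be complete.
3. Optionally, repeat the placebo-based and tipping-point imputations on all randomized subjects with a baseline MADRS score.
4. Report the excluded subjects by arm, cohort and reason (not dosed, or no post-baseline data).

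Cost: one population flag, some wording, a few extra tables, and slightly lower response rates in any arm that regains subjects.
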